#### **12.4.5 Determination of Patients/Data for Analysis**

All randomized subjects in the modified intention-to-treat cohort will be included in the analysis.

#### **12.4.6 Sample Size**

There will be at least 78% power to test this objective provided at least 70 subjects undergo randomization.

The sample size calculation is based on the following assumptions:

- 1:1 randomization
- Constant randomization rate over 16 months
- Last enrolled subject followed through 6 months post-procedure
- 50% chronic treatment success in the PVI only arm versus 75% in the Treatment arm (equivalent to a hazard ratio of 0.415) through 6 months post-procedure
- Constant hazard ratio over all follow-up
- Cumulative alpha of 0.05. Any planned interim analyses will be constructed so that the overall Type I error of the study is no greater than 0.05.
- Constant attrition (dropout) of 5% per 6 months

The sample size calculation was performed in PASS 2008 using the log-rank (Lakatos) procedure. Accounting for a study attrition rate of up to 5% per 6 months ensures that the study will maintain the planned power of 78% in case attrition is higher than expected (approximately 1% per 6 months).

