## 1.2 Study description

The study is expected to be conducted at up to 12 centers located in The United States and up to three centers in Europe. Up to 245 subjects will be enrolled in the study to ensure there are 70 randomized subjects. The number of enrollments permitted relative to the number of subjects to be randomized is high since it is expected that a fair number of subjects will not meet all screening criteria (rigorous blood pressure monitoring and renal anatomy) once consented. Center randomization will be capped at 50% (35) of the total randomized subjects.

Randomized study subjects will be followed for a minimum of six months, and then every six months thereafter until official study closure as determined by Medtronic and/or regulatory authority, whichever occurs first. Accordingly, the expected total study duration is approximately fifty-seven months, representing approximately fifty-one months of enrollment and six months of subject follow-up after the last patient has undergone the study procedure.

Interim analyses of the primary effectiveness objective will take place and if data are deemed to sufficiently characterize this study objective by the sponsor

at one of these analyses, enrollment may be stopped.

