#### **12.4.4 Analysis Methods**

A log-rank test will be used to perform this hypothesis test. The log-rank test uses the time that each subject is free from chronic treatment failure, defined from the date of procedure to the date of chronic treatment failure, if it occurs, or latest of the following: a) the last follow-up visit date, or b) the last date on which AF was assessed, if chronic treatment failure does not occur during the subject's study follow-up. Subjects will be included through all available study follow-up.

In addition to the log-rank test, Kaplan-Meier curves will be used to estimate the rate of chronic treatment success. Cox proportional hazards regression will be used to estimate the hazard ratio and its 95% confidence interval between study arms.

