15.0	Table 1	Revised Study sponsors and contacts	Updated information	47
15.0	Section 5.2.2	Removed exclusion criteria for pacemakers and defibrillators	Supports a larger cohort of patients contributing to enrollment	47
15.0	Section 5.2.2 and 6.12	Added the maximum renal artery diameter acceptable for the exclusion criteria	Typo	47

Version	Applicable Sections	Change	Rationale	Number of subject enrolled
15.0	Section 6.5 and 6.18.2	Allow a CareLink transmission from the subject's home as a substitution for an in-office device interrogation	Clarification	47
15.0	Section 7.1 and 7.3	Changed pedal to switch	Typo	47
15.0	Section 7.2, Table 7 and Appendix F	Added Freezor MAX	Clarification	47
15.0	Section 10	Modified risks to align with the current Arctic Front Advance IFU and added that the current Arctic Front Advance IFU should be referenced with respect to the possible risks	Updated to reflect recently approved labeling for the commercialized device	47
15.0	Section 12.3	Added text to the Safety Composite Event definition	Clinical Events Committee clarification request	47
15.0	Appendix E	Participating investigators, institutions and IRB/MECs updated to current status	New Information	47
16.0	Table 1	Revised Study sponsors and contacts	Updated information	55
16.0	Table 2	Revised Study Core Labs	Updated information	55
16.0	Table 3	Revised Committee contact information	Clarification of Steering Committee	55
16.0	Section 1.2	Revised Study description	Updated expected total study duration and months of enrollment given time needed to reach required subject treatment numbers	55
16.0	Section 1.2	Revised Study description	Updated to include provisions for the conduct of interim analyses	55

Version	Applicable Sections	Change	Rationale	Number of subject enrolled
16.0	Section 2	Revised section to include recently published renal denervation study results	New information	55
16.0	Section 2	Included use of Arctic Front Advance Pro Cardiac Cryoablation Catheter	AFA Pro recently granted FDA approval and CE mark	55
16.0	Table 4	Added Model Number(s) for AFA Pro Cardiac Cryoablation Catheter	AFA Pro recently granted FDA approval and CE mark	55
16.0	Section 3.2	Included use of Arctic Front Advance Pro Cardiac Cryoablation Catheter	AFA Pro recently granted FDA approval and CE mark	55

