5.1. Study Design Summary

The Symplicity AF study is a prospective, randomized, multi-center, investigational, feasibility, clinical study. The study is expected to be conducted at up to 12 centers located in The United States. Up to 245 subjects will be enrolled in the study to ensure there are 70 randomized subjects. The number of

enrollments permitted relative to the number of subjects to be randomized is high since it is expected that a fair number of subjects will not meet all screening criteria (rigorous blood pressure monitoring and renal anatomy) once consented. Center randomization will be capped at 30% (21) of the total randomized subjects.

Randomized study subjects will be followed for a minimum of six months, and then every six months thereafter until official study closure as determined by Medtronic and/or regulatory authority, whichever occurs first. Accordingly, the expected total study duration, if the study conducts a final analysis, is approximately fifty-seven months, representing approximately fifty-one months of enrollment and six months of subject follow-up after the last patient has undergone the study procedure. The figure below illustrates the study design.

Interim analyses of the primary effectiveness objective may take place and if data are deemed to sufficiently characterize this study objective by the sponsor at one of these analyses, enrollment may be stopped.

Figure 1. Study Design Flowchart

Two interim analyses are planned. The first analysis will be conducted after 32 subjects are randomized and have completed their six-month visit. If the primary effectiveness objective is not passed after this analysis, the second will be conducted after 50 patients have been randomized and have completed their six-month visit. If neither interim analysis results in a successful primary effectiveness objective, the final analysis will be conducted once 70 patients are randomized and have completed their six-month visit.

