The original sample size calculation was performed in PASS 2008 using the log-rank (Lakatos) procedure. Updates to incorporate interim analyses were performed using EaST, version 6.4.1 with the survival module. Accounting for a study attrition rate of up to 5% per 6 months ensures that the study will maintain the planned power of 78% in case attrition is higher than expected (approximately 1% per 6 months).

A summary of the EaST output detailing the analyses is given on the following page.

Design: Survival Endpoint: Two-Sample Test - Parallel Design - Logrank Given Accrual Duration and Study Duration

Test Parameters	
Design ID	Des3
Design Type	Superiority
Number of Looks	3
Test Type	2-Sided
Specified α	0.05
Power	0.786
Model Parameters	
HR = λ_c/λ_e	
Under H0	1
Under H1	0.415
Ratio of % Surv. at Period #1:	1.5
Cum. % Surv. by Time =	6
Control (S_c)	50
Treatment (S_e)	75
Var (Log HR)	Null
Allocation Ratio (n_e/n_c)	1
Boundary Parameters	
Spacing of Looks	Unequal
Efficacy Boundary	Interp.
Accrual / Dropouts Parameters	
Cum % Accrued	100
Accrual Duration	16
Max Study Duration	22
Dropout	Yes

Variable Follow-Up Design: All subjects are followed until failure, drop out or end of study.

Sample sizes and events have been rounded.

Sample Size Information

	Control Arm	Treatment Arm	Total
Sample Size (n)			
Maximum	34	35	69
Expected H1	31.666	31.666	63.331
Expected H0	34.288	34.288	68.577
Events (s)			
Maximum	25	16	41
Expected H1	22.52	13.022	34.031
Expected H0	20.325	20.325	40.62
Dropouts (d)			
Maximum	2	3	5
Expected H1	1.723	2.547	4.27
Expected H0	1.985	1.985	3.97
Maximum Information (I):			10.25

Accrual and Study Duration

	Accrual Duration	Study Duration
Maximum	16	21.998
Expected H1	14.686	19.024
Expected H0	15.902	17.361

Stopping Boundaries: Look by Look

Look #	Info. Fraction (s/s_max)	Events (s)	Cumulative α Spent	Boundaries
Efficacy Z				
Upper		Lower		
1	0.341	14	0.01	2.576 -2.576
2	0.463	19	0.015	2.611 -2.611
3	1	41	0.05	2.049 -2.049

Events, Sample Size, Dropouts, Pipeline and Analysis Times: Look by Look (Under H0)

Look #	Info. Fraction (s/s_max)	Sample Size (n)	Events (s)	Dropouts (d)	Pipeline (n-s-d)	Analysis Time	Boundary Crossing Prob (Incremental)
Efficacy							
Upper		Lower					
1	0.341	39	14	2	23	8.863	0.005
2	0.463	46	19	2	25	10.639	0.003
3	1	69	41	4	24	17.481	0.017

Events, Sample Size, Dropouts, Pipeline and Analysis Times: Look by Look (Under H1)

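### The power calculation still assumes 16 months of accrual and a 22-month study, while the plan now expects 51 and 57 months; the stated 41 events and 78.6% power are not those of the described trial, though the error is conservative

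*Protocol*

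**What the plan says.** **Timetable.** Protocol 1.2 states that "the expected total study duration is approximately fifty-seven months, representing approximately fifty-one months of enrollment and six months of subject follow-up" after the last procedure. SAP 5.1 agrees for a study that runs to its final analysis: it "is approximately fifty-seven months, representing approximately fifty-one months of enrollment and six months of subject follow-up". The change history in Protocol Appendix I gives the reason for the version 16 update: "Updated expected total study duration and months of enrollment given time needed to reach required subject treatment numbers".

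**Power calculation.** Protocol 12.4.6 and SAP section 6 both list "Constant randomization rate over 16 months" among the assumptions. The EaST output in SAP section 6 has "Accrual Duration 16" and "Max Study Duration 22". From these it derives 41 maximum events (25 control, 16 treatment), looks at 14, 19 and 41 events, and 78.6% cumulative power. SAP Table 1 splits that power into 17.6%, 10.1% and 50.9% by look.

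**What enters the test.** Protocol 12.4.4 says "Subjects will be included through all available study follow-up". Protocol 12.8 and SAP 7.8 set the looks by the number of subjects who have completed the 6-month visit (32, 50 and 70). SAP 7.8 also leaves out of the assessment anyone who has not reached 6 months.

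**The concern.** Both documents contain both timetables, and no text reconciles them. Version 16 of the protocol updated the duration in 1.2 and also revised the assumptions in 12.4.6, the latter to allow for interim analyses. The accrual input stayed at 16 months.

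If the final analysis were triggered by the 41st event, accrual length would change only the calendar date of the analysis. Here the trigger is 70 completers and subjects contribute all their follow-up, so slower accrual gives early subjects more time at risk and produces more events. Expected events, information fractions, per-look power and cumulative power therefore all depend on an input that the plan no longer holds. These are the figures from which a sponsor or monitoring committee would judge how mature the data are at each look.

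**Working it through.** **Inputs, all from Protocol 12.4.6 and SAP section 6.** Success at 6 months is 50% v 75%, hazards are constant, dropout is 5% per 6 months, allocation is 1:1, and the last subject is followed for 6 months. N is 69 in EaST and 70 in the text. Z boundaries are 2.576, 2.611 and 2.049.

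Monthly hazards:
- control: ln 2 / 6 = 0.1155
- treatment: −ln 0.75 / 6 = 0.0479
- dropout η: −ln 0.95 / 6 = 0.00855
- hazard ratio: 0.0479 / 0.1155 = 0.415, as stated

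**Formula for expected events in an arm.** With n subjects, event hazard λ, κ = λ + η, uniform accrual over A months and total duration T:

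E = n × (λ/κ) × [1 − (e^(−κ(T−A)) − e^(−κT)) / (κA)]

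**Step 1: reproduce the plan (A = 16, T = 22, n = 34.5 per arm).**
- Control: κ = 0.1241, λ/κ = 0.931. E = 34.5 × 0.931 × [1 − (0.475 − 0.065)/1.985] = 25.5
- Treatment: κ = 0.0565, λ/κ = 0.849. E = 34.5 × 0.849 × [1 − (0.7125 − 0.2885)/0.904] = 15.5
- Total 41.0, which matches EaST's 25 + 16 = 41.

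The log-rank drift is |ln 0.415| × √(events/4). At 14 events it is 0.879 × 1.871 = 1.645, so the first-look power is Φ(1.645 − 2.576) = 0.176, as in Table 1. Integrating over all three looks gives 0.176 + 0.101 + 0.509 = 0.786. The plan's figures are therefore correct for a 16/22-month trial.

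**Step 2: change only the timetable (A = 51, T = 57).**
- Control: 34.5 × 0.931 × [1 − (0.475 − 0.001)/6.328] = 29.7
- Treatment: 34.5 × 0.849 × [1 − (0.7125 − 0.0399)/2.881] = 22.4
- Total 52.2 (52.9 with N = 70).

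The final-look drift is 0.879 × √(52.2/4) = 3.18. The final look alone gives Φ(3.18 − 2.049) = 0.87. All three looks give 0.284 + 0.252 + 0.344 = 0.88 by formula. An 8,000-trial log-rank simulation with the tabulated p-value boundaries gives 0.86 (0.78 at 16/22 months). Two-sided type I error with the same boundaries is about 0.048.

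**Step 3: look timing.** With uniform accrual of 70 subjects, the m-th subject completes 6 months at A × m/70 + 6.

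| | First look | Second look |
|---|---|---|
| EaST under H1 | month 10.5, 14 events (0.341) | month 12.6, 19 events (0.463) |
| 32 and 50 completers, A = 16 | month 13.3, about 16 events (0.38) | month 17.4, about 27 events (0.66) |
| 32 and 50 completers, A = 51 | month 29.3, about 21 events (0.39) | month 42.4, about 36 events (0.67) |

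The fractions in brackets are events at the look divided by final events. The looks in EaST already differed from the completer-based looks at 16 months, because EaST times them by events. On the current timetable the 41st event would be expected at about month 46, before accrual ends.

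**Step 4: sensitivity (assumptions not in the documents).** If no events are counted beyond a subject's month 24, the two timetables give 41.6 v 49.4 events and final-look power of 79% v 85%. With a cap at month 12 they give 37.4 v 39.1 events and 74% v 76%. If all hazard starts after the 90-day blanking period, with the same 6-month rates, they give 49.0 v 58.6 events and 85% v 91%. In every case the longer timetable has at least as much power as the shorter.

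**The case against.** The strongest reply is that nothing the plan promises is broken. Both documents claim at least 78% power, and under the plan's own assumptions the longer timetable delivers more. No boundary needs changing and type I error stays below 0.05. Sixteen months is a declared assumption of a calculation that reproduces exactly. The protocol also says that the estimated success rates will inform a pivotal trial whether or not the test is significant. All of this stands, and it limits the finding to consistency. It does not remove it: a declared assumption that the same documents contradict still gives the wrong event count, information fractions and per-look power.

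Three stronger readings are tempting, and the documents do not support them.

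- **The trial is underpowered.** The mismatch works the other way under the stated constant hazard ratio.
- **Longer follow-up pushes power below 78% because the effect may fade.** Fading is an outside assumption. If the hazard ratio returns to 1 after month 12, simulated power is about 69% at 16 months and 63% at 51. If it returns to 1 after month 6, power is about 36% and 32%. Most of the shortfall comes from the fade itself, which would affect the 16-month design too. The long tail also carries little weight: about 4.4 of the 52.9 expected events (8%) fall after a subject's month 22, and Protocol 6.24 allows exit when the monitor's battery ends after 6 months of follow-up.
- **The changed duration caused the look timings to be wrong.** They were already mismatched at 16 months, because EaST counts events and the plan counts completers.

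**Conclusion.** The inconsistency is real, appears in both documents and is not reconciled. The stated 41 maximum events, 78.6% cumulative power and per-look power belong to a 16/22-month trial. The trial as described would yield about 52 to 53 events and about 86 to 88% power, roughly 11 to 12 more events and 8 to 9 more percentage points. This rests on the plan's rates, constant hazards over all follow-up, 5% dropout per 6 months, uniform accrual and unchanged boundaries. The error is conservative, and the claim of at least 78% remains literally true under those assumptions. The point is worth correcting because it concerns the power statement for the primary effectiveness endpoint and is cheap to fix. It does not threaten the validity of the test.

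**What to change.** Rerun the calculation with 51 months of accrual and 57 months in total, and place the looks at 32, 50 and 70 six-month completers so that the information fractions match Protocol 12.8 and SAP 7.8. Changing the two durations alone would leave the look mismatch in place. Then restate the accrual assumption, expected events, information fractions, per-look power and cumulative power together in Protocol 12.4.6, SAP section 6, SAP Table 1 and the EaST output.

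Optionally, add one sentence saying that the extra power depends on the hazard ratio staying constant over the longer follow-up. A figure for a fading effect would be a sensitivity analysis and is not a required correction.

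The cost is one software rerun and matching edits in two documents. Sample size, visits and boundaries can stay as they are.

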### **12.5 Secondary objective**

#### **12.5.1 Single Procedure Chronic Treatment Success**

The secondary effectiveness objective characterizes the rate of chronic treatment success in Treatment and Control arms in the subgroup of subjects that do not undergo an additional pulmonary vein ablation procedure during the 90-day blinded follow-up period.

#### **12.5.2 Hypothesis**

There is no hypothesis for this objective.

#### **12.5.3 Performance Requirements**

There is no performance requirement for this objective.

#### **12.5.4 Analysis Methods**

Kaplan-Meier curves will be used to estimate the rate of chronic treatment success for each study arm. Cox proportional hazards regression will be used to estimate the hazard ratio and its 95% confidence interval between study arms.

#### **12.5.5 Determination of Patients/Data for Analysis**

All randomized subjects in the modified intention-to-treat cohort that do not undergo a permissible repeat cryoablation will be included in the analysis.

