### **6.21 Permissible repeat ablation**

All subjects may have one repeat ablation procedure within Days 0-90 after the first ablation if the following criteria are met:

- Inclusion criteria:
  - Recurrent or a new onset atrial tachycardia

- Exclusion Criteria:
  - Active systemic infection
  - Condition where manipulation of the catheter within the heart would be unsafe (e.g. intracardiac mural thrombus)
  - Cryoglobulinemia
  - Myocardial infarction, unstable angina pectoris, syncope, PCI/PTCA, or coronary artery stenting within 3 months of the repeat ablation
  - Cerebrovascular accident or TIA within 1 month of the repeat ablation
  - Presence or a permanent pacemaker, biventricular pacemaker, atrial defibrillator or any type of implantable cardiac defibrillator (with or without biventricular pacing function)
- Re-ablation assessment is performed as follows:
  - Physical examination, NYHA cardiac functional class, office blood pressure and review of medications and symptoms.
  - Study status post re-ablation: The subject's procedures and follow up visit/assessments will continue based on the initial cryoablation procedure date. A re-ablation of a study subject under this section is not an AF Intervention.

Other ablation techniques may be used as outlined in Section 6.10.

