### **12.4 Primary effectiveness objective**

The primary effectiveness objective compares the rate of chronic treatment success between study arms. Chronic treatment success is freedom from chronic treatment failure. Therefore, comparing the rate of chronic treatment success is equivalent to comparing the risk of chronic treatment failure.

Chronic treatment failure is defined as the occurrence of either

- 1) a documented episode of AF recorded on Reveal LINQ
- 2) an intervention for AF

occurring after a blanked follow-up period of 90 days from the study treatment procedure. AF episodes and repeat ablations that occur within 90 days of the study treatment procedure will not constitute chronic treatment failure.

Intervention for AF is defined as an invasive procedure intended for the definitive treatment of AF, including any ablation of the pulmonary veins or atrial triggers (other than protocol-specified ablation), interruption of AV nodal function, procedures to alter left atrial conduction or function such as the Maze procedure, or the implantation of an atrial pacemaker or atrial defibrillator; whether approved by relevant regulatory authorities or not for such indications; excluding electrical or pharmacologic cardioversion of arrhythmias and excluding procedures solely directed at the treatment of atrial flutter or atrial tachycardias.

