7.1.3. Analysis Sets

Cut-off dates will be applied to the study data when creating snapshots for study reporting. The analysis sets will be created from the applicable snapshot (e.g., for final report).

Enrolled

Patients who signed informed consent and met inclusion/exclusion criteria. Deviations and adverse events will be reported for all enrolled subjects. Enrolled subjects will be included in the CONSORT flow diagram.

Randomized

Enrolled subjects who are randomized.

Modified intent-to-treat

A modified intention-to-treat (mITT) analysis will be performed for the primary objectives. The mITT analysis set will include all randomized subjects that undergo a pulmonary vein isolation procedure (i.e. have a cryocatheter inserted). Patients that are randomized, but exit the study without undergoing a pulmonary vein isolation procedure will not be included in the mITT analysis set. Patients that are randomized to the treatment arm, but do not have the renal denervation procedure, will not be included in the mITT analysis set.

This analysis set is used for the following objectives described previously in Section 4:

- Primary safety

- Primary effectiveness
- Ancillary Objective 1
- Ancillary Objective 2
- Ancillary Objective 3
- Ancillary Objective 4
- Ancillary Objective 6

Secondary Objective

All subjects in the mITT cohort (i.e. subjects used for the Primary Effectiveness Objective) that do not undergo an additional pulmonary vein ablation procedure during the 90 day blanked follow-up period will be included the analysis of the secondary objective.

Ancillary Objective 5

The following subjects will be included in the analysis of ancillary objective 5:

- All subjects in the mITT cohort (i.e. subjects used for the Primary Effectiveness Objective) that do not undergo an additional pulmonary vein ablation procedure during the 90 day blanked follow-up period will be included this analysis

AND

- Have not used Class I and III anti-arrhythmic drugs following the blanking period

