7.10.3.3. Endpoint Definition

The endpoint for this objective is the primary effectiveness endpoint, chronic treatment success, as defined in section 7.10.2.3.

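### The single-procedure success objective drops subjects re-ablated during blanking instead of counting them as failures, so its rate is conditional on no re-ablation and its between-arm comparison is not a randomised one

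*Protocol*

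**What the plan says.** **Analysis set.** CIP 12.5.1 describes the population as the "subgroup of subjects that do not undergo an additional pulmonary vein ablation procedure during the 90-day blinded follow-up period" (blinded there evidently means blanked, the SAP's word). CIP 12.5.5 puts it as "All randomized subjects in the modified intention-to-treat cohort that do not undergo a permissible repeat cryoablation will be included in the analysis". SAP 7.1.3 takes "All subjects in the mITT cohort (i.e. subjects used for the Primary Effectiveness Objective) that do not undergo an additional pulmonary vein ablation procedure" in the blanking period.

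**Endpoint.** SAP 7.10.3.3 adds nothing for a second procedure: "The endpoint for this objective is the primary effectiveness endpoint, chronic treatment success, as defined in section 7.10.2.3". CIP 12.4 says of that endpoint: "AF episodes and repeat ablations that occur within 90 days of the study treatment procedure will not constitute chronic treatment failure". CIP 6.21, which allows one repeat ablation in days 0–90, adds: "A re-ablation of a study subject under this section is not an AF Intervention".

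**When a repeat ablation can happen.** The inclusion criterion in CIP 6.21 is "Recurrent or a new onset atrial tachycardia". Under CIP 6.9, subjects and center staff are blinded only until the index pulmonary vein isolation is done.

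**Analysis.** CIP 12.5.4 plans Kaplan-Meier curves by arm and a Cox hazard ratio with a 95% confidence interval. SAP 7.10.3.4 adds a log-rank test between arms, and SAP 7.9 adds interaction tests. CIP 12.5.2 and 12.5.3 set no hypothesis and no performance requirement.

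**The concern.** A subject who had a second pulmonary vein ablation did not succeed with a single procedure. Under this plan that subject leaves both the numerator and the denominator. The primary endpoint also ignores blanking-period re-ablation, so no planned effectiveness analysis counts it against either arm. If renal denervation reduced early re-ablation, the objective whose title suggests it would show this could not.

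The comparison between arms has a second problem. Whether a subject is re-ablated is settled after randomisation, after an early arrhythmia has been seen, and possibly with the arm known. The subjects who remain are selected on something that treatment, or knowledge of treatment, may influence. A hazard ratio and p-value from such a set can be read as randomised evidence when they are not.

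The practical stake is planning. The study is meant to inform the design of a pivotal trial (CIP 12.4.2), and a conditional success rate taken as a single-procedure rate would make those assumptions too optimistic.

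**Working it through.** **1. The plan's own figures.** Neither document gives a rate, power or sample size for the secondary objective. The only success rates are those behind the primary sample size (CIP 12.4.6): 50% Control and 75% Treatment at 6 months. The stated hazard ratio follows: ln(0.75)/ln(0.50) = (−0.2877)/(−0.6931) = 0.415. The SAP's cumulative power also reproduces: simulating looks at 14, 19 and 41 events with Z boundaries 2.576, 2.611 and 2.049 gives 78.6%. Nothing in the sample size is disputed. Below, 50% and 75% are borrowed as illustrative values of S, the success rate among subjects *not* re-ablated; the CIP assumes them for the whole randomised cohort.

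**2. What happens to one re-ablated subject.**

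| Analysis | In the set? | Re-ablation scored as failure? |
|---|---|---|
| Primary (CIP 12.4, 12.4.5) | Yes | No |
| Secondary (CIP 12.5.5, SAP 7.1.3) | No | No |

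**3. Identity.** Let r be the share of an arm re-ablated in days 0–90. If those subjects stay in and count as failures, single-procedure success is (1 − r) × S. The exclusion rule reports S. The excess is S − (1 − r)S = r × S, which is never negative. It is exact for Kaplan-Meier with the failure placed at day 91 if nobody is censored earlier; otherwise r is the share among those still at risk at day 91.

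**4. Size of the excess.** The documents give no r, so this is a range of assumptions.

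| r (each arm) | Subjects per 35 | Control: reported → all mITT | Excess (points) | Treatment: reported → all mITT | Excess (points) |
|---|---|---|---|---|---|
| 0% | 0 | 50.0 → 50.0 | 0 | 75.0 → 75.0 | 0 |
| 5% | 1.75 | 50.0 → 47.5 | 2.5 | 75.0 → 71.25 | 3.75 |
| 10% | 3.5 | 50.0 → 45.0 | 5 | 75.0 → 67.5 | 7.5 |
| 20% | 7 | 50.0 → 40.0 | 10 | 75.0 → 60.0 | 15 |

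**5. The between-arm difference when r differs.** With S held at 50% and 75%, the subset always shows 25 points. Counting re-ablation as failure gives:

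- r = 20% Control, 5% Treatment: 40.0% v 71.25%, 31.25 points.
- r = 5% in both: 47.5% v 71.25%, 23.75 points.
- r = 5% Control, 20% Treatment: 47.5% v 60.0%, 12.5 points.

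This step only converts one quantity into another. It contains no selection.

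**6. Selection on its own.** Assume half of each arm is high-risk (30% late success) and half low-risk (70%), no treatment effect on late AF, and only high-risk subjects re-ablated: 40% of them in Control (20% of the arm) and 10% in Treatment (5% of the arm).

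- Control subset: (0.5 × 0.6 × 0.3 + 0.5 × 0.7)/(0.30 + 0.50) = 0.44/0.80 = 55.0%.
- Treatment subset: (0.5 × 0.9 × 0.3 + 0.5 × 0.7)/(0.45 + 0.50) = 0.485/0.95 = 51.1%.

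The subset shows Treatment 3.9 points worse although late AF is unaffected. Swapping the re-ablation rates reverses the sign.

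**The case against.** The strongest reply is that the restriction is disclosed and the objective is descriptive. CIP 12.5.1 calls the population a subgroup, there is no hypothesis, and no pass/fail rule, alpha or sample size depends on the result. Success given no repeat procedure is a legitimate quantity, and the all-mITT comparison already exists as the primary analysis. The SAP log-rank test is described only as support.

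Much of this stands, and it limits the weight of the point. It does not remove it. The primary analysis keeps re-ablated subjects but never counts the re-ablation, so it does not supply the missing rate. Calling the set a subgroup does not make a hazard ratio on it a randomised comparison.

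Two stronger inferences are tempting. One is that dropping re-ablated subjects favours Treatment. The documents do not support a direction: if Control subjects were re-ablated more often and had poorer prognosis, removing them would flatter Control, as in step 6. Nor do the documents say that re-ablated subjects would have the worst late AF outcomes; the criterion in CIP 6.21 concerns atrial tachycardia. The other is that a numerical range can be put on the bias in the contrast. That needs re-ablation rates by arm and a model of selection, and the documents give neither.

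**Conclusion.** The point holds for the secondary objective. As written, it reports success conditional on no re-ablation, not single-procedure success in the treated cohort. The excess in each arm is r × S: under the assumed 5–20% re-ablation and 50%/75% success, 2.5–10 points in Control and 3.75–15 in Treatment, and zero if nobody is re-ablated. Those re-ablation rates are assumptions.

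The Cox and log-rank results on the subset are not a randomised comparison, and the direction of their bias is undetermined. A reader should not carry this over to the primary effectiveness decision, its alpha or its sample size, none of which uses this set. The change is worth making because it is small and because these rates are meant to feed a later trial.

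**What to change.** 1. Make the secondary estimate an analysis of all mITT subjects. Count any additional pulmonary vein ablation in days 0–90, by any technique, as a single-procedure failure. Do not count procedures solely for atrial flutter or atrial tachycardia, in line with the exclusion in CIP 12.4.
2. Date that failure at day 91, the first day after blanking. All other failures fall after day 90, and SAP 7.10.9.3 already starts AF burden at the procedure date plus 91. The tied events at day 91 can be handled by the Efron option in the SAP's Cox code.
3. Keep the present subset as a labelled supportive description, with re-ablation counts by arm. Mark any hazard ratio or p-value from it as non-randomised.
4. Align the definitions. CIP 12.5.5 excludes repeat cryoablation, while SAP 7.1.3 excludes subjects by keeping those "that do not undergo an additional pulmonary vein ablation procedure during the 90 day blanked follow-up period", as CIP 12.5.1 does. CIP 6.21 allows other techniques, so a repeat pulmonary vein ablation done without cryoenergy would be kept under one wording and dropped under the other.
5. Review SAP ancillary objective 5, which carries the same exclusion.

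**Cost.** One recoded variable, and amended CIP and SAP wording for an objective that the change history (Appendix I, version 2.0) says was added on the regulator's recommendation. Reported single-procedure success rates will be lower wherever anyone is re-ablated. A remaining limit is that re-ablation can still be decided with the arm known, so the counts by arm should be shown beside the estimate.
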